8.2.3 Exploratory Endpoint

In an exploratory analysis, the duration of the DDT sampling is analysed descriptively using arithmetic mean, standard deviation, median, minimum and maximum values, as well as quantiles, as well as appropriate graphical procedures (e.g., probability density plots, box plots, histograms). To assess the relation between sampling duration and diagnostic accuracy, the duration between positive and negative DDT swabs is compared using a t-test or Mann-Whitney-U test, depending on the distribution of sampling duration, for clinician-positive and -negative swabs, respectively. Additionally, appropriate graphical procedures are used to visualise the relationship between sampling duration and diagnostic accuracy.

8.2.4 Subgroup Analyses

As data from group 1 (participants with a recent diagnosis of HPV) will be collected in the UK and Italy, the sensitivity and specificity for each diagnostic target will be calculated for participants in each country separately and compared between countries using Fisher's exact tests. If the results show no significant differences, the data will be pooled for analysis.

8.4. Analysis Populations

The primary and secondary endpoints will be evaluated using all complete pairs of samples from the Daye diagnostic tampon and clinician collected samples.

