Trial Aims	
 ● To measure the diagnostic accuracy of the diagnostic tampon in a diverse population of people assigned female at birth. ● To compare the performance of the diagnostic tampon with traditional diagnostic methods to identify potential advantages and challenges. ● To assess the acceptability and usability of the diagnostic tampon among the target population and explore feasibility and clinician acceptability of the diagnostic tampon in clinical practice among key stakeholders. ● To provide evidence-based recommendations for the integration and sustainability of the diagnostic tampon into current health practices.
Trial Objectives	
Primary Objective:
 
 ● Evaluate the diagnostic accuracy of the Daye

	
diagnostic tampon for detecting Chlamydia, Gonorrhoea, BV and HPV, specifically demonstrating a sensitivity of more than 70% for DDT.
 
Secondary objectives:
 
 ● Assess the usability of the DDT (via ASQ). ● Explore participants' views of the usability and acceptability of the DDT. ● Assess whether the DDT is a preferred sampling method for participants. ● Assess if the order of sample collection (self-swab vs DDT) impacts diagnostic accuracy. ● Understand the health economic consequences of using the DDT for STI, BV and HPV testing. ● Explore stakeholder attitudes to tampons as a means of sample collection for microbial testing. ● Assess the occurrence of AEs/SAEs as a result of tampon sampling. 
Exploratory objective:
 
 ● Explore the relationship between duration of wear and diagnostic accuracy.
Sample Size	
350 participants
 
Group 1: 50 participants with a recent confirmed HPV+ diagnosis (UK and Italy)
 
Group 2: 300 participants from the general population (UK only)

Procedures	
All participants will have 3 samples taken: the DAYE Diagnostic Tampon (DDT), a vaginal self-swab and a clinician taken vaginal swab that is validated for use for the downstream microbial test.

Randomisation	
All participants will be randomised using block randomisation according to sample order for the DDT and self-swab:
 
 ● Group A: Approximately half the participants will perform the self-swab followed by the DDT. ● Group B: Approximately half the participants will perform the DDT followed by the self-swab

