2. OBJECTIVES AND OUTCOME MEASURES

Primary Objective

Objective	Outcome Measure	Timepoint(s) of evaluation
Evaluate the diagnostic accuracy of the Daye Diagnostic Tampon for detecting Chlamydia, Gonorrhoea, BV and HPV, specifically demonstrating a sensitivity of more than 70% for DDT.	Accuracy of the STI, BV and HPV testing using menstrual tampons compared to other specimen collection methods (clinician taken and self-swab) using the following assays: 
 - Hologic's APTIMA HPV (for HPV) - Hologic's APTIMA AC (for chlamydia and gonorrhoea) - Cepheid MPV assay (for BV) 	Within 4 weeks of the samples being received at the lab.

Secondary Objectives

Objective	Outcome Measure	Timepoint(s) of evaluation
Assess the usability of the DDT (via ASQ)	After scenario questionnaire scores	Post-sampling (once all samples are collected)
Explore participants views of the usability and acceptability of the DDT	Quantitative and qualitative feedback from pre- and post-sampling questionnaires and focus groups	Pre-sampling (baseline) and Post-sampling (once all samples are collected)
Assess whether the DDT is a preferred sampling	User preferences (self-report)	Pre-sampling (baseline) and Post-sampling (once

method for participants		all samples are collected)
Assess if the order of sample collection (self-swab vs DDT) impacts diagnostic accuracy	Diagnostic accuracy	Post sample analysis
Understand the health economic consequences of using the DDT for STI, BV and HPV testing	Willingness to pay for the DDT, comparison of time taken for DDT vs clinician swab	Post-sampling (once all samples are collected)
Explore stakeholder attitudes to tampons as a means of sample collection for microbial testing.	Qualitative feedback from stakeholder questionnaires	Ongoing throughout the trial once stakeholders have engaged with the tampon
Assess the occurrence of AEs/SAEs as a result of tampon sampling.	AE/SAE occurrence.	None expected, but any events will be collected and recorded on an ongoing basis as outlined in section 7.

Exploratory Objective

Objective	Outcome Measure	Timepoint(s) of evaluation
Explore the relationship between duration of wear and diagnostic accuracy.	Duration of DDT wear and diagnostic accuracy	Post sample analysis

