7.3. Procedures for Reporting Adverse Events

We do not anticipate that the trial procedures (DDT or swabs) should result in any adverse events (AEs) but include this section in case such events are reported so that they can be considered for causal links to the trial procedures. Only AEs that are clinically judged by the research site PI as being caused by the trial procedures (related and unexpected) will be reported to the REC that gave favourable opinion.

Participants will be provided with contact information for the trial team and the clinic nurse in the event that they need to report a side effect or medical event from the DDT, self-swab or clinician swab.

Events related to the trial procedures will be collected from the collection of the first trial sample until the final questionnaire is submitted.

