8.2.2 Secondary Endpoints

The secondary endpoints will be assessed by analysing the items of the questionnaires descriptively at each assessment point in time (pre-sampling and post-sampling). A change score will be calculated for continuous items assessed both pre-sampling and post-sampling, and appropriate statistical methods are used to compare pre- to post-sampling values (e.g., t-test for repeated measurements, Wilcoxon signed-rank test). For categorical items, the absolute and relative frequency of each answer option will be reported, as well as the change between categories pre- and post-sampling where feasible.

The *Occurrence of AEs/SAEs* will be analysed descriptively by indicating the absolute and relative frequency of each AE/SAE over the course of the trial duration.

To assess whether the order of sampling influences the diagnostic accuracy, sensitivity and specificity of self-swabs and DDT are compared using McNemar tests for clinician-swab-positive and -negative samples, respectively. Additionally, Cohen's kappa will be calculated to assess the concordance of results from self-swabs and DDT.

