8.7. The Level of Statistical Significance

Effects are considered statistically significant if the associated two-tailed p -value is less than 5%.

8.8. Procedure for Accounting for Missing, Unused, and Spurious Data.

As per section 8.4 data will only be used for analysis if none of the required values for the respective analysis is missing. Swabs not yielding a conclusive result will also be excluded. Participants who provide swab results, but have missing pre- or post-sampling questionnaires will not be excluded from the analysis population. The number of missing values and inconclusive results will be reported for each sample (Daye diagnostic tampon swabs, self-swabs, and clinician collected samples). Missing data will not be replaced for analysis.

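### Section 8.4 ties every secondary endpoint to a complete DDT/clinician sample pair, so read literally it removes adverse events and usable questionnaire answers from participants without one

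*Protocol*

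**What the plan says.** The only analysis population in the protocol is in section 8.4: "The primary and secondary endpoints will be evaluated using all complete pairs of samples from the Daye diagnostic tampon and clinician collected samples". It has no exceptions. Section 8.1 confirms that section 8 is the whole analysis plan.

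Section 2 lists among the secondary objectives "Assess the occurrence of AEs/SAEs as a result of tampon sampling" and "Assess whether the DDT is a preferred sampling method for participants", together with ASQ usability, acceptability, willingness to pay and stakeholder attitudes. Section 8.2.2, under the secondary-endpoint heading, gives the AE summary as the "absolute and relative frequency of each AE/SAE over the course of the trial duration", without naming a denominator. It also states that "Cohen's kappa will be calculated to assess the concordance of results from self-swabs and DDT".

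Section 8.8 opens by referring to 8.4, requires that the values needed for a given analysis be present, and excludes inconclusive swabs. Its one explicit protection is: "Participants who provide swab results, but have missing pre- or post-sampling questionnaires will not be excluded from the analysis population". The reverse case, a participant with a questionnaire or an event but no valid pair, is not mentioned.

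**The concern.** A sample pair is the right unit for sensitivity and specificity. It is the wrong unit for a safety count or a questionnaire item. For AEs the restriction can also be informative: a reaction to the tampon, or failure to insert or retain it, can be the reason why the pair is missing. Conditioning on a complete pair then selects people in whom the device worked, and the AE frequency is likely to be too low. Questionnaire answers and DDT/self-swab pairs would also be discarded for a reason unrelated to whether they are usable.

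**Working it through.** No stated figure is in dispute, so the check is mainly textual. The arithmetic at the end is illustrative.

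**1. Can an event be recorded in someone without a pair?** Yes. Section 7.3 says: "Events related to the trial procedures will be collected from the collection of the first trial sample until the final questionnaire is submitted". Collection therefore starts before any pair exists. In the central/clinic-list schedule (5.1.1), the DDT is used about a day before the visit at which the clinician swab is taken and the DDT handed in. Section 5.15 stops assessments at withdrawal. A participant who has a DDT event and leaves before that visit has a recorded AE and no pair. In the Italian in-clinic schedule (5.1.2) the clinician swab comes first, so a participant who returns the DDT and then leaves keeps the pair.

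**2. Are incomplete pairs expected?** Yes. Section 8.3 enlarges the sample partly for samples that go missing, are lost or give no clear result. It states no rate.

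**3. Which secondary analyses need the DDT/clinician pair?**

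| Analysis | Data needed | Fit with 8.4 |
|---|---|---|
| AE/SAE frequency | Any trial sampling started | Too narrow |
| Questionnaire items | An answer to the item | Too narrow |
| Stakeholder questionnaire (5.13.2) | Reply from a healthcare worker, who gives no samples | Cannot apply |
| Kappa, DDT v self-swab | DDT and self-swab | Drops pairs without a clinician result |
| McNemar, within clinician-positive and -negative | All three samples | Consistent; 8.8 adds the self-swab |

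**4. Size for AEs (all rates assumed).** Let d be the share without a pair, p1 the AE proportion with a pair and p0 the proportion without. Section 8.4 reports p1. Among all N = 350 (8.3), taking all to have started sampling, the proportion is (1 − d)·p1 + d·p0. The share of events dropped is d·p0 divided by that.

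| d | p1 (reported under 8.4) | p0 | All participants | Events dropped |
|---|---|---|---|---|
| 10% | 1% | 1% | 1.0% | 0.35 of 3.5 (10%) |
| 2% | 1% | 10% | 0.98×0.01 + 0.02×0.10 = 1.18% | 0.7 of 4.13 (17%) |
| 10% | 1% | 50% | 0.90×0.01 + 0.10×0.50 = 5.9% | 17.5 of 20.65 (85%) |
| 2% | 2% | 10% | 0.98×0.02 + 0.02×0.10 = 2.16% | 0.7 of 7.56 (9%) |
| 10% | 2% | 50% | 0.90×0.02 + 0.10×0.50 = 6.8% | 17.5 of 23.8 (74%) |

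The first row shows that the proportion is biased only if events and missing pairs are related.

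**5. Size for preference (assumed).** Suppose 10% lack a pair, 80% of those with a pair prefer the DDT, and none of those without do. Suppose also that everyone with a pair answers and a fraction r of the others answer. The value among all who answer is 0.9×0.80 / (0.9 + 0.1r):
- r = 1: 72.0%
- r = 0.2: 0.72/0.92 = 78.3%
- r = 0: 80%, the same as under 8.4

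Section 5.11 sends the post-sampling questionnaire only after all samples are taken, and 5.15 stops assessments at withdrawal. A low r is therefore plausible for people who could not use the tampon or who left.

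**The case against.** The best defence is that 8.4 speaks of sample pairs and was written with sample-based endpoints in mind. Section 8.8 asks only for the values that each analysis needs, and a sample pair is not needed for an AE count. The literal reading also fails for the stakeholder questionnaire. This has force: the authors may not have intended the literal rule. But 8.8 introduces its rule by pointing to 8.4, which names the secondary endpoints expressly, and there is no other document to settle the matter. An analyst who follows 8.4 as written would exclude these people.

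Several further points stand and limit the finding:
- A reader might infer that usability and preference are materially inflated. Sections 5.11 and 5.15 do not support that, because many people who could not use the tampon or who left would have no post-sampling ratings under any analysis set. The answers that 8.4 itself discards are mainly those of people with lost or inconclusive samples, and nothing links those losses to tolerance of the tampon.
- A reader might infer that events go unrecorded. They do not: collection and reporting under section 7 are unaffected, and only the descriptive frequency is at risk.
- A reader might infer that everyone who leaves after an event is dropped. The Italian in-clinic schedule shows otherwise.
- A reader might infer that the McNemar tests use the wrong set. They condition on the clinician result, so they need the clinician sample as well as the other two.
- Section 8.8 already reports missing and inconclusive samples by type, including the DDT.

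**Conclusion.** The point holds as a conflict between 8.4 and 8.8 and as a badly fixed analysis set. As written, 8.4 removes AEs in participants without a valid pair, discards answered questionnaire items from participants with a missing, lost or inconclusive sample, and excludes from kappa the DDT/self-swab pairs without a clinician result. For AEs the likely direction is understatement, on the assumption that tampon problems are one cause of missing pairs. The size cannot be determined: the protocol gives neither an AE rate nor an incomplete-pair rate, and it anticipates no AEs from the procedures (7.3). The figures above show only what the assumed rates would imply. Any effect on usability and preference is probably smaller. The accuracy analyses, for which the pair rule is appropriate, are not touched by this point.

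**What to change.** Rewrite 8.4 by endpoint:
- **Accuracy:** valid DDT/clinician pair, per condition.
- **AEs/SAEs:** all participants who attempted the DDT or had any trial sample taken.
- **Questionnaire items:** all participants who answered the item, whatever their sample status.
- **Kappa:** all valid DDT/self-swab pairs.
- **McNemar:** participants with all three samples valid for the condition.

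Align 8.8 with this, including the reverse case that it now omits. Present the missing-DDT count that 8.8 already provides next to the usability results, since inability to supply a sample bears on usability and the questionnaire may not capture it.

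The cost is a wording amendment, with no new data and no extra participants. Denominators will differ by endpoint and must be shown, and the reported AE figures may be slightly less favourable. The change will not recover ratings from people who never received or completed the post-sampling questionnaire.

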8.5. Subgroup Analyses

The primary and secondary endpoints will be assessed for each group separately as exploratory subgroup analyses.

8.6. Decision Points

One interim analysis on the primary endpoints may be performed once 35 participants of group 1 and 215 participants of group 2 have been evaluated. The interim analysis is conducted to assess the prevalence of each condition within the respective group and

the sample size will be adjusted to meet the determined number of participants with the respective condition if needed.

8.7. The Level of Statistical Significance

Effects are considered statistically significant if the associated two-tailed p -value is less than 5%.

8.8. Procedure for Accounting for Missing, Unused, and Spurious Data.

As per section 8.4 data will only be used for analysis if none of the required values for the respective analysis is missing. Swabs not yielding a conclusive result will also be excluded. Participants who provide swab results, but have missing pre- or post-sampling questionnaires will not be excluded from the analysis population. The number of missing values and inconclusive results will be reported for each sample (Daye diagnostic tampon swabs, self-swabs, and clinician collected samples). Missing data will not be replaced for analysis.

8.9. Procedures for Reporting any Deviation(s) from the Original Statistical Plan

Any deviations from the statistical procedures laid out in this document and their reasons will be recorded in an amendment to this document.

9 DATA MANAGEMENT

The data management aspects of the trial are summarised here with details fully described in the Data Management Plan.

9.1. Source Data

Source documents are where data are first recorded, and from which participants' CRF data are obtained. These include, but are not limited to, hospital records (from which medical history may be summarised into the CRF), participant questionnaires and correspondence.

EDC entries will be considered source data if the EDC is the site of the original recording. All documents will be stored securely and safely in confidential conditions.

9.2. Access to Data

Data will be entered into a validated EDC platform. Direct access to the EDC platform will be granted to delegated site users. Access will also be granted to authorised representatives from the Sponsor and Lindus Health to allow trial-related monitoring and/or audits to ensure compliance with regulations. Access to this system will be strictly on a need to know basis and the system will be on a secure server. In Italy some data may be entered onto paper CRFs before being transcribed into the EDC platform. Access to the paper documents will be strictly on a need to know basis and these documents will be stored in an access controlled room. To ensure data transparency, the trial will be registered on a publicly available database for clinical studies.

9.3. Data Recording and Record Keeping

The data management will be run in accordance with Lindus Health SOPs, which are fully compliant with Good Clinical Practice (GCP), GDPR and the Data Protection Act 2018.

Research data will be de-identified upon collection. Identifiable information will be stored separately from the research data.

A unique trial specific number and/or code in the database will be used to identify the participants. Where necessary for trial conduct the participants name, date of birth and address will be shared with third parties and vendors who require these details for the logistics of trial conduct.

An online secure data entry system (Citrus) designed to collect sensitive data, such as participant contact details, will be used. All identifiable participant data is encrypted using the Advanced Encryption Standard. Citrus will also manage online ePRO.

Informed consent (e-consent) will be completed using worksheet templates, online or in person, which will be retained in a secure area with restricted access. The remaining data, including reconfirmation of consent and records of eligibility confirmation will be collected directly onto the EDC platform, therefore no further source will be available. In Italy some data may be entered onto paper CRFs before being transcribed into the EDC platform.

Identifiable participant data will be kept for 12 months beyond the end of the trial. Non-identifiable participant data will be maintained for a minimum of ten years unless otherwise required to comply with legislation or regulation and reviewed on an annual basis.

10 QUALITY ASSURANCE PROCEDURES

10.1. Risk assessment

A risk assessment and monitoring plan will be prepared before the trial opens and will be reviewed as necessary over the course of the trial to reflect significant changes to the protocol or outcomes of monitoring activities.

Risk Mitigation:

The trial will be conducted in accordance with the current approved protocol, GCP, relevant regulations and Standard Operating Procedures. All site staff will receive training in trial procedures according to GCP where required.

10.2. Monitoring

Regular monitoring will be performed according to GCP using a risk-based approach. In the UK, Lindus Health will be responsible for the monitoring of all aspects of the trial's conduct and progress and will ensure that the protocol is adhered to, and that appropriate action is taken to safeguard participants and the quality of the trial itself. In Italy, the sponsor will be responsible for the monitoring of all aspects of the trial's conduct and progress and will ensure that the protocol is adhered to, and that

appropriate action is taken to safeguard participants and the quality of the trial itself. The level of monitoring required will be informed by the risk assessment.

Please refer to the trial Monitoring Plan(s) for further details.

10.3. Trial Operations Group

There will be a central trial team, composed of representatives from DAYE (Tampon Innovations Ltd), Lindus Health and the Italian site who will meet regularly to monitor trial progress. There will be no other trial committees.

11 PROTOCOL DEVIATIONS

A trial related deviation is a departure from the ethically approved trial protocol or other trial document or process (e.g. consent process) or from Good Clinical Practice (GCP) or any applicable regulatory requirements. Any deviations from the protocol will be documented and filed in the trial master file.

A Lindus Health SOP is in place describing the procedure for identifying non-compliances, escalation to the central team and assessment of whether a non-compliance /deviation may be a potential Serious Breach.

12 SERIOUS BREACHES

A serious breach is defined as “A breach of GCP or the trial protocol which is likely to affect to a significant degree –

- (a) the safety or physical or mental integrity of the participants of the trial; or
- (b) the scientific value of the trial”.

In the event that a serious breach is suspected the Sponsor must be contacted within 1 working day. In collaboration with the CI the serious breach will be reviewed by the Sponsor and, if appropriate, in the UK the CRO (Lindus Health) will report it to the REC committee, Regulatory authority and the relevant host organisations according to local regulatory timelines. In Italy the serious breach will be reported to the ethics committee and regulatory authority by the sponsor.

